11.1.1 Calculation of MCID

Anchor-based calculation of MCID: Change scores for clinical outcomes will be determined by subtracting the initial result from the post-programme result for each participant.

After completing the clinical assessments at the 3-month and 6-month follow up points participants will be asked to provide a global rating of change in their score for each scale by answering the following question: "Has there been any change in your walking ability/walking distance/daily activities etc since the last test?". Participants will be asked to respond on a transitional 3-point scale as follows: 1, worse; 2, about the same; 3, better. If they indicate no change, the patient will be given a score of 0. If they indicate there has been an improvement or deterioration, they will be asked to score their change on the following 15-point Likert scale [3, 4]:

-7, a very great deal worse; -6, a great deal worse; -5 a good deal worse; -4, moderately worse; -3, somewhat worse; -2 a little worse; -1, almost the same, hardly any worse at all; 0, no change; 1, almost the same, hardly any better at all; 2, a little better; 3, somewhat better; 4, moderately better; 5, a good deal better; 6 a great deal better; and 7 a very great deal better.

Scores of -1, 0 and 1 will be considered no change, scores of 2 to 3 small improvement and scores of 4 to 7 substantial improvement [4].

Correlations will be determined for participant self-assessment of performance scores and change in clinical outcomes. Correlations will be determined for the RA assessment of the participant's performance and change in clinical outcomes. The mean change in scores for patients scoring no change, small improvement and substantial improvement will be compared by ANOVA. The sensitivity and specificity for change in score to distinguish patients classified as changed (≥ 2) from those whose performance was unchanged (-1 to +1) will be calculated and a receiver operating characteristic (ROC) curve obtained [5]. The data point corresponding to the upper left corner of the curve will represent the MCID.

11.1.2 Sensitivity analysis

As a sensitivity analysis the MCID will be calculated using a distribution based approach.

Distribution-based calculation of MCID: The standard error of measurement (SEM) for all patients scoring will be used to estimate the MCID based on the following equation: $SEM=\sigma_1 \times V(1-r)$, where σ_1 is the baseline standard deviation and r represents the intraclass correlation coefficient (ICC), which is a measure of the test-retest reliability of the scale. The ICC will be calculated using the baseline and post-treatment scores for each participant at post-programme evaluation. Using this method, one SEM represents the estimated MCID [6].

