2.3 Trial Flowchart

2.4 Trial Statistics

The analysis will be conducted according to the intention to treat. The primary outcome will be analysed using multiple regression with the baseline 6MWD value and the stratification factor, centre, included as covariates. Results will be reported as the difference in mean 6MWD between the intervention and control groups with a 95% confidence interval (CI). Other continuous outcomes will be similarly analysed. Logistic regression will be used to analyse binary outcomes, with the models including the stratification factor, centre, as a covariate. The sensitivity and consistency of the EQ-5D-5L will be analysed using correlations with VascuQoL-6 and other clinical measures.

Two analytical methods will be applied to calculate the MCID:

1. Anchor-based calculation of MCID: Change scores for clinical outcomes will be determined by subtracting the initial result from the post-programme result for each participant. Correlations will be determined for participant self-assessment of performance scores and change in clinical outcomes and the RA assessment of the participant's performance and change in clinical outcomes. The mean change in scores for patients scoring no change, small improvement and substantial improvement will be compared by ANOVA. The sensitivity and specificity for change in score to distinguish patients classified as changed (≥ 2) from those whose performance was unchanged (-1–1) will be calculated and a ROC curve obtained (Deyo et al., 1991). The data point corresponding to the upper left corner of the curve will represent the MCID. 2. Distribution-based calculation of MCID: The standard error of the mean (SEM) for all patients scoring will be used to estimate the MCID based on the following equation: SEM= σ 1×V(1-r), where σ 1 is the baseline standard deviation and r is test-retest reliability of the scale. The intraclass correlation coefficient for test-retest reliability will be calculated using the baseline and post-treatment scores for each participant at post-programme evaluation. Using this method, one SEM represents the estimated MCID (Wyrwich et al., 1999).

3. Sample Size, Selection and Withdrawal of Participants

Participants and recruitment: Potentially eligible adults will be identified by one of two methods which can proceed in parallel and are described below:

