5.3.2 Primary

6 Minute Walking Distance (6MWD in metres) is measured during a self-paced, standardised 6 Minute Walking Test (6MWT) conducted around a level, 100-foot circuit [1, 2]. During the 6MWT, maximal walking ability (time (seconds) walked before resting) and pain free walking ability (time (seconds) walked before reported pain onset) will be measured. Pain intensity will also be measured before and after the walking test using the Claudication Pain Scale. The walk test is completed twice, with the results from the best test (i.e. the highest 6MWD) used for analysis; using the highest 6MWD is based on the American Thoracic Society guidelines for the 6MWT [2].

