7.2 Secondary Endpoints

The difference in mean walking ability at 6 months between the intervention and comparison groups, adjusted for baseline walking ability and site.

The difference in QoL at 6 months between the intervention and comparison groups, adjusted for baseline QoL and site.

The difference in activities of daily living at 6 months between the intervention and comparison groups, adjusted for baseline activities of daily living and site.

The MCIDs for the following measures will be calculated: 6MWD, SR-MWD, WELCH, NEADL, VascuQol-6.

8 Sample Size Considerations

Based on previous work, 192 participants will be required to detect a mean 6MWD difference of 58 metres (standard deviation (SD) =111; α =0.05; 1- β =0.90) accounting for 20% attrition at 3 months follow up.

9 Analysis Sets

The definitions of different analysis populations are shown below:

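### The distribution-based MCID takes its test-retest reliability from scores on either side of the intervention, so real change is counted as measurement error and the MCID is expected to come out too large

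*SAP*

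**What the plan says.** SAP 11.1.2 sets the standard error of measurement (SEM) equal to the baseline SD times the square root of 1 minus r, where "r represents the intraclass correlation coefficient (ICC), which is a measure of the test-retest reliability of the scale". On the source of r it says: "The ICC will be calculated using the baseline and post-treatment scores for each participant at post-programme evaluation". The rule for the MCID follows: "Using this method, one SEM represents the estimated MCID". Protocol 2.4 has the same instruction: "The intraclass correlation coefficient for test-retest reliability will be calculated using the baseline and post-treatment scores for each participant at post-programme evaluation".

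The method's standing is given at the start of SAP 11.1.2: "As a sensitivity analysis the MCID will be calculated using a distribution based approach". The main MCID is the anchor-based one in SAP 11.1.1, read from a ROC curve. SAP 7.2 lists the scales: "The MCIDs for the following measures will be calculated: 6MWD, SR-MWD, WELCH, NEADL, VascuQol-6".

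Two other parts of the plan bear on a remedy. SAP 11.1.1 collects a participant rating of change for each scale and defines a stable band: "Scores of -1, 0 and 1 will be considered no change". SAP 5.3.2 provides a repeat test for 6MWD: "The walk test is completed twice, with the results from the best test (i.e. the highest 6MWD) used for analysis". Neither is used for the ICC. Neither document says whether the ICC is a consistency or an absolute-agreement coefficient.

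**The concern.** The SEM formula isolates measurement error only if r comes from repeated measurements of people whose true state has not moved. Here the two measurements bracket a 12-week treatment period (SAP 4.1 and 4.3), and with 1:1 allocation half the participants receive an intervention intended to shift the score. Anyone who truly improves or declines lowers r, as does the difference in mean change between arms. The SEM then contains part of the effect under study, and the threshold for judging a benefit tends to rise with the benefit observed.

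MCID values are secondary objective 3. The distribution-based figure is the SAP's only cross-check on the anchor-based figure. If it is contaminated by treatment effect, neither agreement nor disagreement between the two can be read plainly.

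**Working it through.** **Inputs from the documents.** SD 111 m, difference 58 m, alpha 0.05, power 0.90 and 20% attrition (SAP section 8; protocol section 3). Tests are two-sided (SAP 10.1) and allocation is 1:1 (SAP section 3).

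**Assumptions.** The documents give none of these: 111 m is the baseline SD; true test-retest reliability R lies between 0.80 and 0.95; true individual change has SD s between 0 and 70 m and is unrelated to baseline; MOSAIC adds 58 m and usual care adds nothing.

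**Step 1: the plan's own figure.** No ICC, SEM or MCID value is stated, so only the sample size can be reproduced. Per arm, n = 2 × [111 × (1.95996 + 1.28155) / 58]² = 76.97. For two arms this is 153.94, and 153.94 / 0.80 = 192.4, against the stated 192. The inputs are consistent.

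**Step 2: formulas.** Let V = 111² = 12,321.
- Post-treatment variance: V1 = V + s² + 58²/4, where 58²/4 = 841 is the variance created by a 58 m difference between two equal arms.
- Covariance of the two scores: R × V.
- Consistency ICC = R × V / [(V + V1)/2].
- Agreement ICC: the same, with 29²/2 = 420.5 added to the denominator, because the mean shift over both arms is 29 m.
- SEM = 111 × √(1 − ICC).

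**Step 3: R = 0.90.** R × V = 11,088.9, and the SEM from true reliability is 111 × √0.10 = 35.1 m.

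| Real change present | ICC form | Denominator | ICC | SEM |
|---|---|---|---|---|
| 58 m effect only | consistency | 12,741.5 | 0.870 | 40.0 m (+14%) |
| 58 m effect only | agreement | 13,162 | 0.842 | 44.1 m (+26%) |
| s = 40 m, no effect | either | 13,121 | 0.845 | 43.7 m (+24%) |
| 58 m effect, s = 40 m | consistency | 13,541.5 | 0.819 | 47.2 m (+35%) |
| 58 m effect, s = 40 m | agreement | 13,962 | 0.794 | 50.4 m (+43%) |

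The last three rows show the dependence on the treatment effect: with s fixed at 40 m, adding the 58 m effect raises the SEM from 43.7 m to 47.2 or 50.4 m. A simulation with 154 completers gave matching averages for the four rows with the effect (40.0, 44.0, 47.2 and 50.2 m).

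**Step 4: the range with the 58 m effect.**
- Smallest inflation: R = 0.80, s = 0, consistency. ICC = 9,856.8 / 12,741.5 = 0.774. SEM = 52.8 m against 49.6 m, or 1.06 times.
- Largest inflation: R = 0.95, s = 70 m, agreement. V1 = 12,321 + 4,900 + 841 = 18,062; denominator = 15,191.5 + 420.5 = 15,612; ICC = 11,704.95 / 15,612 = 0.750. SEM = 55.5 m against 24.8 m, or 2.24 times.

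**Step 5: is the direction certain?** No. Suppose R = 0.90, there is no treatment effect, and true scores spread by 10% in proportion to baseline. The covariance is 1.1 × 11,088.9 = 12,197.8, V1 = 1.21 × 11,088.9 + 1,232.1 = 14,649.7, and the consistency ICC is 12,197.8 / 13,485.3 = 0.905. The SEM is 34.3 m, slightly below 35.1 m. Adding the 58 m effect raises the mean variance to 13,905.8, lowers the ICC to 0.877 and gives 38.9 m, which is again inflated.

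**The case against.** The strongest reply is about weight. The SAP makes this a sensitivity analysis. The anchor-based MCID, the primary 6MWD comparison, the power calculation and the secondary between-arm comparisons do not use this ICC. That stands, and it limits the severity.

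A reader might infer three stronger things that the documents do not support.
- *That all five MCIDs will be too large.* Only 6MWD can be illustrated. No SD or reliability is given for SR-MWD, WELCH, NEADL or VascuQoL-6, and step 5 shows that inflation is the expected direction and not a certainty.
- *That the MCID is roughly doubled.* Factors near 2 need reliability close to 0.95 together with large individual change. At reliability 0.80, the 58 m effect alone adds 6% to 12%.
- *That the MCID would exceed the 58 m the trial is powered for.* This depends on a reliability and a spread of change that the documents do not state. In the R = 0.90 table, every value is below 58 m.

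It might also be said that a consistency ICC removes the problem. It removes only the average shift over all participants. The arm difference (841 m²) and individual change stay in the denominator. Nor can the text be read as already limited to stable patients: the sentence introducing the SEM seems incomplete, but the ICC sentence refers to each participant.

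**Conclusion.** The point holds, at the level of something that should be fixed. SAP 11.1.2 and protocol 2.4 name one quantity, test-retest reliability, and compute another, the agreement between scores before and after treatment. Following the text as written, the distribution-based MCID is expected to be too large, to grow with the treatment effect, and to be a poor check on the anchor-based value.

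For 6MWD the inflation is about 1.06 to 2.24 times. This rests on 111 m being the baseline SD, a 58 m gain in one arm only, true reliability of 0.80 to 0.95, true-change SD of 0 to 70 m, and either ICC form. These sizes are illustrative. The trial's main conclusion is not at risk.

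**What to change.** Replace the ICC sentence in SAP 11.1.2, and bring protocol 2.4 into line, so that:

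1. For each scale, the ICC is computed from baseline and 3-month scores only in participants whose own 3-month rating for that scale lies in the no-change band of SAP 11.1.1 (-1 to 1). At 3 months the preceding assessment is baseline, so rating and score interval match.
2. Both arms pooled give the main estimate; usual care alone is a check.
3. The ICC form is stated, for example two-way, absolute agreement, single measure, and its 95% CI is reported.
4. For 6MWD, the two walks at the baseline visit may give a supplementary estimate only. They omit between-day variation, include learning, and describe a single test, whereas the analysed score is the better of two.

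The cost is SAP wording and a few lines of code, plus keeping both walk distances in the database if item 4 is used. The ratings are already planned. The price is precision and some independence. The stable subset is smaller, so the interval is wider: usual care alone has about 96 × 0.80 = 77 completers before selection. Selecting on the rating also ties the check partly to the anchor it is meant to test. Both limits should be stated with the result.

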11.1.3 Model assumption checks

For the primary analysis, the model assumes that the difference in walking distances between the group receiving MOSAIC and the group receiving usual NHS care are normally distributed. If this is found to be skewed, transformations will be considered. Residuals will be plotted to check for normality and inspected for outliers. Non-parametric tests may be used if the parametric methods do not appear to be appropriate e.g. the assumptions do not appear to hold.

11.1.4 Mediation analysis

If appropriate, a regression based analysis will be performed to explore this.

11.1.5 Subgroup analyses

There are no planned subgroup analyses.

12 Baseline data analysis

Histograms will be produced for continuous variables and summarised using mean, standard deviation, number with median and range if the data are very skewed.

Categorical data will be summarised by frequencies and percentages.

The number of AEs and SAEs will be reported with proportions and 95% confidence intervals for differences between the groups where appropriate.

13 Software

Statistical analysis: Stata 15 or (later if there is an update before analysis), will be used for data analysis.

14 Bibliography

- 1. Montgomery, P.S.a.G., A.W., *The Clinical Utility of a Six-Minute Walk Test in Peripheral Arterial Occlusive Disease Patients.* Journal of the American Geriatrics Society, 1998. **46**(6): p. 706-711.
- 2. Society, A.T., *American Thoracic Society Statement: Guidelines for the Six-Minute Walk Test* American Journal of Respiratory and Critical Care Medicine, 2002. **166**(1).
- Jaeschke; R., S., J., Guyatt, G. H., Measurement of Health Status Ascertaining the Minical Clinically Important Difference Controlled Clinical Trials, 1989. 10(4): p. 407-415.
- 4. Juniper, E.F., et al., *Determining a minimal important change in a disease-specific quality of life questionnaire.* Journal of Clinical Epidemiology, 1994. **47**(1): p. 81-87.
- Deyo, R.A., P. Diehr, and D.L. Patrick, *Reproducibility and responsiveness of health status measures statistics and strategies for evaluation*. Controlled Clinical Trials.
 12(4): p. S142-S158.
- 6. Wyrwich, K.W., W.M. Tierney, and F.D. Wolinsky, *Further Evidence Supporting an SEM-Based Criterion for Identifying Meaningful Intra-Individual Changes in Health-Related Quality of Life.* Journal of Clinical Epidemiology, 1999. **52**(9): p. 861-873.

	Who	When	How	To Whom
SAE	Chief Investigator	-Report to Sponsor within 24 hours of learning of the event -Report to the MREC within 15 days of learning of the event	SAE Report form for Non- CTIMPs, available from NRES website.	Sponsor and MREC

Appendix 1 – Information with regards to Safety Reporting in Non-CTIMP Research

				A3.213024
Urgent Safety Measures	Chief Investigator	Contact the Sponsor and MREC Immediately	By phone	Main REC and Sponsor
		Within 3 days		
			Substantial amendment form giving notice in writing setting out the reasons for the urgent safety measures and the plan for future action.	Main REC with a copy also sent to the sponsor. The MREC will acknowledge this within 30 days of receipt.
Progress Reports	Chief Investigator	Annually (starting 12 months after the date of favourable opinion)	Annual Progress Report Form (non-CTIMPs) available from the NRES website	Main REC
Declaration of the conclusion or early termination of the study	Chief Investigator	Within 90 days (conclusion) Within 15 days (early termination) The end of study should be defined in the protocol	End of Study Declaration form available from the NRES website	Main REC with a copy to be sent to the sponsor
Summary of final Report	Chief Investigator	Within one year of conclusion of the Research	No Standard Format However, the following Information should be included:- Where the study has met its objectives, the main findings and arrangements for publication or dissemination including feedback to participants	Main REC with a copy to be sent to the sponsor
